9.4. Definition of Analysis Sets

Sets used in the Analyses

Type of analysis	Aim	Definition of analysis set
Primary: ITT patients	Analysis of safety and primary efficacy analysis	All included patients who received at least one dose of fexinidazole.
Secondary: treatment completers	Sensitivity analysis on efficacy	All included patients who completed the treatment period and who received all protocol-planned doses.
Secondary: evaluable patients	Sensitivity analysis on efficacy	ITT patients, except those who died due to causes clearly unrelated to efficacy or safety. Exclusion will be documented.
Secondary: per protocol patients	Sensitivity analysis on efficacy	ITT patients with no major protocol violations. Major violations will be described for each patient.

9.5. Patient Disposition

At the end of the study, patient disposition (overall population and by stage, i.e. stage 1, early stage 2 and late stage 2, at diagnosis) will be presented in terms of:

- Number of patients screened
- Number of patients not included in the study because they did not fulfil the eligibility criteria, and reason for non-inclusion
- Number of patients included
- Number of included patients who received at least one dose of fexinidazole (ITT patients)
- Number of included patients who completed the treatment period and who received all protocol-planned doses (treatment completers)
- Number of included patients who received at least one dose of the IP, except those who died due to causes clearly unrelated to the efficacy or safety of the IP (evaluable patients)
- Number of included patients with no major protocol violations (per protocol patients)
- Number of included patients who attended the following visits: screening visit, baseline assessment, visits during treatment period (D1 to D10), EOT visit, EOH visit, and follow-up visits at 3, 6, 12, and 18 months.

- Number of included patients who were withdrawn from the study, listed by reason for withdrawal
- Number of included patients with at least one protocol violation, listed by nature of violation, i.e. minor or major

9.6. Baseline Data

Descriptive summary statistics (n, mean, standard deviation, median, minimum, maximum) or frequencies and percentages will be presented for the following baseline characteristics of the study population:

- > Demographic data
- Medical history
- Physical examination
- Vital signs
- > Urine pregnancy test (only for girls \geq 12 years of age)
- Laboratory assessments
- ≻ ECG
- Karnofsky Performance Score
- Neurological examination
- Concomitant medication

9.7. Treatment Compliance

The dosing regimen of fexinidazole is described in Section 5 Treatments, p 38.

Treatment compliance will be analysed by describing the number and percentage of patients who completed the treatment period. Patients in whom the treatment period was extended by one day (missed dose made up for at end of treatment) will be considered as having completed the treatment period. For patients who prematurely discontinued treatment, the duration of exposure will be presented.

9.8. Efficacy Analysis

9.8.1. Primary Efficacy Analysis

Primary Efficacy Endpoint

The primary efficacy endpoint is the. success or failure, at 12 months after the final treatment intake. The patient's treatment will be a success if there is no evidence of trypanosomes in any bodily fluid, and the WBC count in the CSF is $\leq 20/\mu$ L. Patients with no parasitological evidence of relapse, but with a CSF WBC count > 20/µL or who, in the opinion of the Investigator, require rescue treatment, will be considered to be probable relapses and therefore as failures. Death due to any cause or use of rescue medication will be considered as a relapse, i.e. a failure. A patient who attends the follow-up visit at 12 months or later and who

refuses to undergo lumbar puncture, but who has no signs or symptoms of HAT and for whom the outcome was assessed as favourable at the last assessment will be considered as a probable cure, i.e. a success, unless signs of relapse are detected on any assessment up to 18 months.

Primary Analysis

The primary analysis will be performed on the ITT population.

The primary endpoint is the success or failure of treatment, as defined above.

The primary analysis of success or failure will be performed at 12 months of follow-up.

The primary test is an exact test derived from the exact confidence interval (CI) of the success rate at 12 months.

Two sets of statistical hypotheses will be tested simultaneously:

 H_{0A} : the true success rate is equal to or less than 80%, which is considered to be unacceptable.

H_{1A}: the true success rate is greater than 80%.

 H_{0B} : the true success rate is equal to or greater than 92%, which is the target or expected success rate for fexinidazole.

H_{1B}: the true success rate is less than 92%.

If H_{0A} is rejected, then the success rate is significantly greater than 80% and the estimated rate is consistent with a rate of 92%. In this case, H_{0B} is automatically accepted, but not necessarily true.

If H_{0B} is rejected, then the success rate is significantly less than the target of 92%, and the estimated rate is consistent with the unacceptable rate of 80%. In this case, H_{0A} is automatically accepted, but not necessarily true.

If the observed success rate is equal to or greater than 87.2% (\geq 109 successes out of 125 patients), or equal to or greater than 110 successes out of 126 patients (if the sample size is equal to 126), then the study is a success since the rate is significantly greater than 80% and consistent with the target success rate of 92%.

Conversely, if the observed success rate is less than 87.2% (\leq 108 successes out of 125patients) or less than 110 successes out of 126 patients, then the study is a failure since the success rate is significantly less than the target rate of 92% and consistent with the unacceptable rate of 80%.

The unacceptable success rate of 80% is greater than the success rate of melarsoprol at 12 months, i.e. 74.8%, because the success rates of the alternative treatments, i.e. NECT and pentamidine, are considerably higher than the rate with melarsoprol, which increases the level of unacceptability.

The target or expected rate of 92% is greater than the expected value of 89% set in the pivotal study, because the success rate is evaluated at 12 months instead of 18 months (expected gain of 1.2%) and also because the success rate reported in the pivotal study is encouraging, since only one failure (a patient whose health status had been poor at inclusion) among 150 patients was observed at the EOT, and no relapses were observed among 30 patients during the 6-month follow-up period (blinded data with an allocation ratio of 2 fexinidazole for 1 NECT).

It should be noted that, in the pivotal study, a 94% success rate was expected for NECT at 18 months, and the margin of acceptable difference was set at 13%. This means that the level of the unacceptable rate for fexinidazole is81% if the success rate for NECT is truly 94%, and 80% if the success rate for NECT was 93%. This also means that the various expectations and limits are consistent across studies.

9.8.2. Sensitivity Analyses

Several sensitivity analyses will be performed to assess the robustness of the results of the primary analysis and to facilitate interpretation. They will be performed on the population of treatment completers, the population of evaluable patients and the per-protocol population. Additional sensitivity analyses will be described in the SAP.

9.8.3. Secondary Efficacy Analyses

- The secondary analysis will be performed on the success rate at month 18.
- determine whether the success rate of treatment with fexinidazole varies depending on the stage of the disease, i.e. stage 1 versus early stage 2 versus late stage 2, using a Fisher exact test to compare the rates observed with the 3 different stages.

If the difference between the 3 stages is significant, then the exact 95% CI of each success rate at 12 months will be calculated, and the stage that is responsible for the heterogeneity will be identified. The stage responsible for the heterogeneity will be separated from the other 2 stages, and the lower limit of the 95% CI of each of the 2 subgroups will be compared to the limit of 75%, which is slight higher than the success rate of melarsoprol at 12 months. A limit lower than 80%, i.e. 75% instead of 80%, was chosen because the sample size in each subgroup will be smaller, which will have an impact on the statistical power of each comparison. The upper limit of the CI of the success rate in patients with stage-1 HAT should be consistent with (greater than or equal to) the rate of 93%, which is the

historical success rate of pentamidine (61). The upper limit of the CI of the success rate in patients with stage-2 HAT should be consistent with the rate of 94%, which is the historical success rate of NECT.

- The correlation between the success rate and the WBC count in the CSF will be estimated using a logistic regression. The WBC count will be a quantitative covariate. Another analysis will be performed using a logistic regression with a random intercept to take into account the centre effect. A trend test will also be performed using the Bartholomew's test. Another analysis will be performed after pooling patients with late stage-2 HAT treated with fexinidazole in the pivotal study with patients in this study. The correlation between the success rate and the baseline WBC count will be adjusted with a logistic regression model using the centre as covariate.
- The time-course of the cumulative rate of definitive failure (from the start
 of treatment to the definitive failure) will be estimated using the KaplanMeier method, and patients lost to follow-up will be considered as
 censures. The success rate at each timepoint will be estimated and
 compared using a Cochran Q-test. The logistic model for repeated
 measures (Glimmix procedure in SAS[®]) will be used to test the time effect
 adjusted by centre.

Data on patients with stage-1 and early stage-2 HAT in the DNDiHATFEX005 study will also be pooled. A logistic model with success at 12 months as the response and stage as covariate, as well as the study, will be used. The main results will concern the homogeneity of the success rates for the various stages. If there is heterogeneity, the success rate in patients with stage-1 HAT should not be lower than the success rate in patients with stage-2 HAT.

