1.12. Rationale for the Study Design

Based on the encouraging efficacy and safety results in adults in the on-going DNDiFEX004 study, it would appear that oral treatment with fexinidazole could be beneficial in children 6 years of age and older. The dosing regimen in children is based on the results in adults (see Section 1.11 Choice of Dosing Regimen and Dose p 27).

This cohort of patients will provide additional efficacy data and, because the levels of systemic exposure in children are similar to those observed in adults, will show that the safety profile of fexinidazole, based on the data currently available, remains favourable.

The present study will be a plug-in to the pivotal DNDiFEX004 study in adults, which means that it will be possible to compare the results in the two studies since patients will be recruited simultaneously, i.e. same centres and investigators, with a genetically homogeneous population. In the same way, it will be possible to compare patients with stage-1 HAT in the present study to patients with stage-1 HAT in Study DNDiHATFEX005.

In order to provide the results within a reasonable timeframe, the study will be open label and will include a total of 125 children 6 years of age or older with a body weight of at least 20 kg. The patients will undergo the same assessments and investigations as the adult patients in Study DNDiFEX004. Under these conditions, if there are no statistically significant differences with regard to the efficacy and safety data, the results of treatment in children will be considered to be equivalent to those in adults. Thus, the number of children needed to treat is lower than if this had been a stand-alone study.

The objective is to be able to administer fexinidazole as a single treatment to all patients with HAT, without recourse to CSF-based staging of the disease. The aim of the present study is to assess the efficacy and safety of fexinidazole in children with stage-1, early stage-2 and late stage-2 HAT, stratified into three sub-groups. The study will provide an assessment of the success rate of treatment overall and by stratum, as well allowing for comparison with historical data on pentamidine in patients with stage-1 HAT.

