2.1.1. Primary Objective

• To demonstrate that the success rate 12 months after the end of treatment in patients with stage-1 or stage-2 HAT is greater than an acceptable rate of 80% and consistent with a target rate of 92%.

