2.1.2. Secondary Objectives

- To verify whether the success rate varies depending on the stage of the disease; if the success rate is significantly different between the 3 strata, to show that the rate is greater than 80% and compatible with the historical success rate reported with NECT in patients with stage-2 HAT and with pentamidine in patients with stage-1 HAT.
- To verify whether the success rate of treatment with fexinidazole varies depending on the WBC count in the CSF prior to treatment initiation.
- To study changes in the success rate over time.

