9.1. Sample Size Determination

Determination of the sample size was based on the primary analysis (see Section 9.8.1 Primary Efficacy Analysis, p 61). With a sample size of 125 patients, the probability of rejecting H_{0A} ($\pi \le 0.8$) is 97.5% if the true success rate is 92% with a one-sided type-I error of 0.025. The probability of rejecting H_{0B} ($\pi \ge 0.92$) is also 97.5% if the true success rate is 80% with a one-sided type-I error of 0.025. The statistical power achieved is slightly higher than the desired power, and the alpha value obtained is slightly lower than the desired value, due to the discrete distribution of the population. The sample size may be 126 patients who received at least one dose of fexinidazole if two patients are recruited simultaneously at the time of study discontinuation. If the sample size exceeds 126 patients, there is a risk of simultaneously rejecting both H_{0A} and H_{0B}. The sample size should not be less than 125 in order to avoid the risk of not rejecting either hypothesis.

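### The stage analysis tests a floor of 75% where the objective states 80%, and stage intervals are planned only after a significant Fisher test

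*Protocol*

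**What the plan says.** The secondary objective on stage (2.1.2) is conditional. If the success rate differs significantly between the three strata, the aim is "to show that the rate is greater than 80% and compatible with the historical success rate reported with NECT" in stage 2 and with pentamidine in stage 1.

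Section 9.8.3 carries this out in steps. A Fisher exact test compares the three observed rates. "If the difference between the 3 stages is significant, then the exact 95% CI of each success rate at 12 months will be calculated". Next, whichever stage is held responsible is separated from the other two. Then "the lower limit of the 95% CI of each of the 2 subgroups will be compared to the limit of 75" per cent. The section states openly that 75% replaces 80% because the subgroups are small, and it places 75% slightly above the melarsoprol rate.

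Two other places bear on this. Section 9.8.1 explains why the overall floor is 80% and not melarsoprol's 74.8%: NECT and pentamidine do considerably better, "which increases the level of unacceptability". Section 1.12 says, without condition, "The study will provide an assessment of the success rate of treatment overall and by stratum".

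**The concern.** The objective and its analysis use different floors, so a subgroup can pass the planned check while the stated objective remains unshown. Low power in a small subgroup is a reason to admit low power. It does not make a rate that 9.8.1 calls unacceptable for the whole trial acceptable for part of it, and 9.8.1 had already argued against a floor near melarsoprol.

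The second issue is the condition on the intervals. The trial aims at one treatment for all patients without CSF-based staging (1.12), so the precision of the late-stage-2 result matters whether or not a heterogeneity test reaches significance. A non-significant three-group test does not show that the stages are alike. Yet in that case the plan calls for no stage interval and no floor check.

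**Working it through.** **Inputs.** From the protocol: 125 patients; floor 80% and target 92% (2.1.1); success at 109 or more of 125 (9.8.1); stage floor 80% (2.1.2) against 75% (9.8.3). The strata are self-weighted (4.2), so no stage sizes are given, and 9.8.3 gives no significance level for the Fisher test. The stage splits, the stage rates and a two-sided level of 0.05 used below are assumptions.

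**1. The plan's own figure.** Section 9.1 says that the probability of rejecting the 80% hypothesis "is 97.5% if the true success rate is 92% with a one-sided type-I error of 0.025". With X binomial on 125 patients, P(X ≥ 109 | 0.80) = 0.0243 and P(X ≥ 109 | 0.92) = 0.978, which agrees with the protocol. The exact interval is 80.05 to 92.5% for 109/125 and 79.1 to 91.9% for 108/125. The primary rule is sound.

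**2. What the change of floor does.** The exact lower limit for x successes in n is the 2.5% quantile of Beta(x, n − x + 1). The smallest x that clears each floor, and the chance of reaching it at a true rate of 92%, are:

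| n | needed for >75% | needed for >80% | chance at 92%, floor 75% | chance at 92%, floor 80% |
|---|---|---|---|---|
| 40 | 36 | 38 | 79% | 37% |
| 60 | 52 | 55 | 95% | 65% |
| 80 | 68 | 72 | 99% | 81% |

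Results between the two thresholds pass 9.8.3 but do not meet 2.1.2. Examples are 52/60 (CI 75.4 to 94.1%) and 38/42 (CI 77.4 to 97.3%). A subgroup truly at 80% clears the 75% floor with probability 12.7% (n = 60) or 16.4% (n = 80), against 1.2% and 1.3% for an 80% floor.

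**3. A trial that the condition leaves without intervals.** Take an assumed split of 42/41/42 (stage 1, early stage 2, late stage 2) with failures of 3, 3 and 10. Total failures are 16, so successes are 125 − 16 = 109 and the trial succeeds. The exact 3×2 Fisher test gives p = 0.053. Late stage 2 is 32/42 = 76.2%, CI 60.5 to 87.9%. The plan then calls for no stage interval and no comparison with any floor.

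**4. How often that could happen.** Full enumeration of the Fisher test together with the primary rule gives the following. Each cell shows Fisher power, then the probability that the trial succeeds and Fisher is non-significant.

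| Split | 95/95/85% | 95/95/80% | 98/98/75% |
|---|---|---|---|
| 42/41/42 | 32%; 67% | 58%; 40% | 95%; 5% |
| 30/20/75 | 25%; 62% | 53%; 24% | 95%; 3% |
| 60/25/40 | 35%; 64% | 60%; 37% | 96%; 4% |
| 20/10/95 | 6%; 59% | 26%; 16% | 78%; 3% |

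In the first three splits, power is about 25 to 60% for a late-stage-2 deficit of 10 to 15 points and about 95% for 23 points. It is lower when late stage 2 dominates, but the primary test then gives some protection: with 75 late-stage-2 patients at 80% and the others at 95%, the trial succeeds only 41% of the time.

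**The case against.** The strongest reply is that the significance condition is part of the objective itself, so 9.8.3 follows 2.1.2 when it waits for a significant Fisher test. That stands: the condition alone is no contradiction, and 1.12 promises an assessment by stratum, not an interval. What remains is that a non-significant result says little about homogeneity at the power shown above, and that an interval for each stage needs no extra patients.

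The 75% is also declared and reasoned, not slipped in. That stands too, but the objective was not changed to match. Nor is a 12.7% pass rate at a true 80% an error of the 75% floor, since 80% does exceed 75%. It matters only when judged against the 80% in the objective.

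A reader might infer more than the documents support:

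- *That a poor late-stage-2 result would stay hidden.* The Fisher test needs the observed stage rates. The regression on CSF white-cell count, the trend test and the pooled analyses with the two sister studies run regardless.
- *That the Fisher test is simply underpowered.* This depends on a stage mix and a deficit that the protocol does not give.
- *That 2.1.2 requires every stage to exceed 80%.* It speaks of the rate after a significant difference, and 9.8.3 applies its floor to two subgroups, one of them pooled.
- *That the upper-limit rule is empty because 16/20 has an upper limit near 94%.* The 94% criterion applies to stage 2 as a whole, not to a stratum of 20, and it stands beside a floor.

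**Conclusion.** Two points hold. First, on the text alone and without assumptions, 2.1.2 states 80% and 9.8.3 tests 75%, so no planned analysis tests the objective as written. The gap is 2 to 4 successes for subgroups of 40 to 80 patients. The 75% anchor also conflicts with the reasoning in 9.8.1.

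Second, exact stage intervals and the floor check depend on a significant Fisher test. How often a successful trial would end without them rests on the assumed splits, rates and 0.05 level: roughly 24 to 67% for deficits of 10 to 15 points in the first three splits, and 3 to 5% for 23 points. The primary analysis is not affected. This is a secondary-analysis defect that should be corrected.

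**What to change.** Report the 12-month success rate with its exact 95% CI for each of the three stages whatever the Fisher result, beside the historical pentamidine or NECT rate. Use the Fisher test to describe heterogeneity, not to decide whether intervals are produced.

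Use one floor in 2.1.2 and 9.8.3: compare the lower limits of the two subgroups with 80%, as the objective states, and describe a result that clears only 75% as not having shown a rate above 80%. Do not impose a formal 80% floor on every single stage, because small stages cannot meet it: 15/15 has a lower limit of 78.2%, and 20 to 25 patients would need zero failures.

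This is a wording change and needs no extra patients. The cost is power: at a true 92%, the chance of clearing the floor falls from 79% to 37% with 40 patients, from 95% to 65% with 60, and from 99% to 81% with 80.

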5.9. Rescue Treatment

Patients who show no clinical response to treatment at the EOT visit, as well as patients with evidence of relapse, i.e. *T.b. gambiense* found in any bodily fluid, or of probable relapse at any time during follow-up will receive NECT, an alternative treatment for HAT, as per usual practice in the investigational centre.

The definition of probable relapse disclosed at the 6-month, 12-month or 18month follow-up visit is provided in Table 1.

Rescue treatment for HAT will not be recorded in the "Concomitant Treatment" section of the eCRF, but will be recorded as a comment on the "End of Study" page with the date of treatment start.

Table 1 – Clinical Management of Patients

Visit	Ideal timing of visit after end of treatment	Success	Probabale success	Probable failure	Proven failure
24 hours after EOT	Within 2 days	• Patient alive with no evidence of trypanosomes in any bodily fluid (54)			 Evidence of trypanosomes in any bodily fluid
3 months	3 months ± 1 week	 Patient alive with no evidence of trypanosomes in any bodily fluid (no lumbar puncture at 3 months unless Investigator suspects a relapse) 	 Any reason leading the Investigator to request an additional follow-up visit 	 Signs or symptoms suggestive of HAT and of treatment failure leading to use of rescue treatment 	 Evidence of trypanosomes in any bodily fluid
6 months	6 months ± 2 weeks	 Patient alive with no evidence of trypanosomes in any bodily fluid and CSF WBC ≤ 20/µL 	 CSF WBC between 20 and 50/µL and additional follow-up visit requested within 1 to 3 months Any reason leading the Investigator to request an additional follow-up visit 	 CSF WBC ≥ 50/µL (36) Neurological signs or symptoms leading to use of rescue treatment 	 Evidence of trypanosomes in any bodily fluid
12 months	12 months ± 4 weeks	 Patient alive with no evidence of trypanosomes in any bodily fluid and CSF WBC ≤ 20/µL 	 CSF WBC > 20/µL and clinically non-significant increase as compared to previous value(s) CSF WBC > 20/µL and < 50/µL and reduced as compared to previous value(s) Any reason leading the Investigator to request an additional follow-up visit within 1 to 3 months 	 CSF WBC ≥ 50/µL Signs or symptoms suggestive of HAT and of treatment failure leading to use of rescue treatment 	 Evidence of trypanosomes in any bodily fluid

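### The baseline CSF WBC analysis in 9.8.3 uses an outcome that itself contains CSF WBC, so it cannot separate more relapse from incomplete clearance of cells

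*Protocol*

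**What the plan says.** The secondary objective in 2.1.2 is "To verify whether the success rate of treatment with fexinidazole varies depending on the WBC count in the CSF prior to treatment initiation". Section 9.8.3 addresses it as follows: "The correlation between the success rate and the WBC count in the CSF will be estimated using a logistic regression". The count enters as a quantitative covariate, with no scale given. The same section adds a random-intercept model for centre, Bartholomew's trend test, and a model pooled with late stage-2 patients from the pivotal study.

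The outcome is the success defined in 2.2.1 and 9.8.1: alive, no trypanosomes in any fluid, and CSF WBC at most 20/µL at 12 months. Section 9.8.1 addresses children who miss only the count limb: "Patients with no parasitological evidence of relapse, but with a CSF WBC count" above 20/µL "will be considered to be probable relapses and therefore as failures".

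Table 1 in section 5.9 sorts some of the same children differently. Its 12-month column for probable success includes a count above 20 and below 50/µL ("and reduced as compared to previous value(s)"), and a count above 20/µL with a clinically non-significant increase.

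The stage definitions in 1.13 and 4.2 put every stage-1 and early stage-2 child at or below 20/µL at entry. Section 4.2 leaves the stage mix to recruitment.

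**The concern.** Predictor and outcome share a measurement. A child who starts at or below 20/µL already meets the count limb and can miss it at 12 months only if the count rises. A child who starts well above 20/µL must come down to it, and for the same proportional fall the highest starters are the most likely to stay above the limit. Incomplete clearance of baseline cells thus adds failures only at the upper end of the predictor.

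Sections 1.12 and the Protocol Summary give the aim as one treatment for all patients without CSF-based staging. A positive WBC result would be read as evidence against that aim. As planned, the analysis cannot say whether it reflects more relapse at high counts or slower normalisation of the count. With few failures expected, a handful of count-only cases can decide the result.

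**Working it through.** **1. The plan's own figure.** Section 9.1 states: "With a sample size of 125 patients", the probability of rejecting a rate of 80% or less "is 97.5% if the true success rate is 92% with a one-sided type-I error of 0.025". Section 9.8.1 sets the rule at 109 or more successes.
- Exact type-I error: P(X ≥ 109 | n = 125, p = 0.80) = 0.0243.
- Exact power: P(X ≥ 109 | n = 125, p = 0.92) = 0.978.
- Lower 95% exact limit: 80.05% for 109/125 and 79.1% for 108/125.

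The primary design is reproduced. The protocol gives no comparable figure for the WBC analysis.

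**2. Number of failures.** At the 92% target, 125 × (1 − 0.92) = 10. This is the only event count that follows from the document.

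**3. How the association arises.** Write the 12-month count as baseline × r, where r is the fraction remaining. The count limb is failed when r > 20/baseline. For a baseline of 20/µL or less this needs r > 1, that is, a rise. For a baseline of 40 it needs r > 20/40 = 0.5; for 400, r > 20/400 = 0.05. No relapse is involved in this step.

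**4. What the stated analyses separate.** The models in 9.8.3 all use the composite success. The sensitivity analyses named in 9.8.2 change the population (completers, evaluable, per protocol), not the outcome.

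**5. Size, by simulation.** Each trial has 125 children and 10 failures. Of these, s are count-only failures drawn from children with baseline above 20/µL; the rest are drawn at random, unrelated to baseline WBC. The model is logit P(success) = b0 + b1 × baseline WBC, tested by Wald and likelihood ratio, with 1,500 trials per scenario. The following are assumptions, because the protocol does not give them:
- s = 3 to 5 of 10;
- two-sided alpha 0.05;
- stage 1/early 2/late 2 mix of one third each, 50/20/30, 25/15/60 or 10/10/80%;
- late-stage counts log-normal, median 100 (log SD 1.0) or 200 (log SD 0.8);
- count-only failure either equally likely for every child above 20/µL, or proportional to baseline count.

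Share of trials with p < 0.05, raw count, range over mixes, distributions and both tests:

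| Assumed mechanism | s = 3 | s = 5 |
|---|---|---|
| Equally likely above 20/µL | 3% to 13% | 5% to 28% |
| Proportional to baseline count | 14% to 41% | 34% to 75% |
| All scenarios | 3% to 41% | 5% to 75% |

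For s = 4 the overall range is 4% to 61%. On the log scale the ranges are 3% to 35% (s = 3) and 4% to 84% (s = 5).

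The upper end is not a ceiling. A separate simulation (late-stage median 120) gave all children the same average proportional fall, with log-normal variation between them. It returned 39% to 77% with about 3 count-only failures and 61% to 95% with about 5.

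**6. The same regression without count-only failures.** Between 10 − 5 = 5 and 10 − 3 = 7 failures remain. p < 0.05 then occurs in about 2% to 4% of trials (Wald) or 5% to 8% (likelihood ratio), close to nominal. Bartholomew's test and the random-intercept model were not simulated.

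**The case against.** The best defence is that the analysis answers its own question. The objective concerns the success rate, success is defined to include the count, and 2.2.1 and 9.8.1 regard a count above 20/µL as probable relapse. If children with high baseline counts miss that definition more often, success does vary with baseline WBC. This stands: the association is real for the composite and misleads only if read as more parasitological or clinical relapse.

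A reader might infer that a false WBC finding would occur in roughly 25% to 50% of trials. The documents do not support that figure. It appears in one assumed scenario (25/15/60% mix, median 100, proportional mechanism: 25% to 26% at s = 3, 50% to 51% at s = 5). Under the equally-likely mechanism with mostly late-stage children there is almost no inflation. The figure of 3 to 5 count-only failures is itself assumed.

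A reader might also infer that the count should be dropped from the main outcome for this objective. That has its own bias. Some count-only failures may be true relapses detected first by the count. A child given rescue treatment on count alone could be scored a success, which pushes the result towards no dependence. Only about 5 to 7 events might remain.

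Table 1 also matters: if its 12-month category decides the analysed outcome, many slow clearers become successes and the effect shrinks. Finally, 9.8.3 attaches no threshold or decision to this analysis, 9.8.2 leaves further sensitivity analyses to the SAP, and section 10.2 has a committee check the consistency of success and failure rules. These points lower the stakes. They do not separate the two explanations in the analysis the protocol already fixes.

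**Conclusion.** The structural point holds on the text alone. The outcome in 9.8.3 includes the 12-month value of the measurement whose baseline value is the predictor, and only children above 20/µL at entry can fail by incomplete clearance of baseline cells. The planned analyses cannot tell this from dependence of relapse on baseline WBC.

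The size is not derivable from the protocol. In the main simulation grid, with about 10 failures of which 3 to 5 are assumed count-only, the chance of p < 0.05 on the raw count runs from about nominal to about 75%; other scales or mechanisms go higher. It rests on the assumed stage mix, WBC distribution, clearance mechanism and alpha.

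Sections 2.2.1 and 9.8.1 also conflict with Table 1 on children with a falling count between 20 and 50/µL at 12 months, so the outcome is ambiguous for exactly these children. The point concerns a secondary analysis; the primary endpoint and its decision rule are unaffected.

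**What to change.** In 9.8.3:
- Keep the composite outcome as the planned analysis for the WBC objective.
- Add a supportive logistic model and trend test in which count-only failures are not counted as failures.
- State the analysis rule for children given rescue treatment on count alone, for example analysing them both ways.
- Tabulate count-only failures by baseline WBC and by stage.
- State that a WBC association will be interpreted as more relapse only if it is also seen without the count-only failures, and note the low number of events.

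Separately, reconcile 2.2.1 and 9.8.1 with the 12-month probable-success category in Table 1, so that each child has one analysed outcome.

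The cost is a few lines of text, one supportive model with its trend test, and one table. The supportive model will have low power, with perhaps 5 to 7 events, and should be reported with its confidence interval.
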